10.2 Demographics, baseline assessments, and subject characteristics

Demographic endpoints and subject characteristics will be presented by investigational product using descriptive statistics.

10.3 Efficacy analysis

All analyses will be performed by treatment group and in total.

The GAIS assessment will be presented in frequency tables at each follow-up visit and for each evaluator separately (/Investigator). In addition, the proportion of improved subjects (assessed as very much improved, much improved or improved) will be presented together

The subject satisfaction questionnaire assessments will be presented in frequency tables at each applicable visit. For the questions where the answer is given using an agreement scale the number and percentage of subjects agreeing (Definitely agree/Somewhat agree) to the assessment will also be presented.

The evaluation of naturalness, will be presented in frequency tables at each follow-up visit and for each evaluator separately /Investigator).

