7.1 General information

The methods for collecting efficacy data include 2D photography (section 7.2), GAIS (section 7.3), naturalness (7.4), subject satisfaction questionnaire (7.6), and a section 4.7).

At treatment visits, all assessments must be performed before study treatment is administered.

To avoid inter-observer variability, every effort should be made to ensure that the same individual who made the initial screening or baseline determinations completes all corresponding follow-up evaluations.

7.2 2D Photography

Photographs shall be taken prior to the injections of the investigational product when applicable and at follow-up visits in order to document treatment effect.

Note that no covering make-up shall be used on the photographs.

At visits where injections are performed, the photographs shall be taken prior to the injections and should include a front, 45°-front lateral, and profile picture.

Instructions for photography are provided in a separate photography manual. Each photograph shall be labelled with the subject number, and the visit number at which the photograph was taken. In order to maintain confidentiality, the photographs must not include any information that may reveal the subject's identity. The photographs should be used in the assessment of GAIS,

AEs. The photographs shall be presented on a computer monitor (preferably the same monitor throughout the study).

Photographs shall be taken at the time points indicated in the schedule of events (section 4.7).

Doc id 05DF1910 Clinical Study Protocol 👶 GALDERMA MA-42248

Global Aesthetic Improvement Scale (GAIS)

The GAIS is a qualitative 5-graded scale evaluating aesthetic improvement (Table 3). While GAIS is neither an objective measurement tool nor a validated tool, GAIS improvement has been commonly accepted by the medical community in Europe and the United States as clinical meaningful scale to assess visible aesthetic results. The GAIS can be used not only by the Investigator, but is also a useful tool for

Table 3. Global Aesthetic Improvement Scale (GAIS)

Rating (for the CCI)	Description (for the Investigator and CCI)
Very much improved	Optimal cosmetic result for the subject.
Much improved	Marked improvement in appearance from the original condition, but not completely optimal for this subject.
Improved	Obvious improvement in appearance from the original condition.
No change	The appearance is essentially the same as the original condition.

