Worse	The appearance is worse than the original condition.

Source: Adapted from Narins et al. 200311.

and Investigator shall, independently of each other, rate the lower face for aesthetic change by comparing the appearance at follow-up against a photograph taken before treatment. The photographs shall be presented on a computer monitor (preferably the same monitor throughout the study). The Investigator will perform a live assessment . The following question will be asked: "How would you

describe the subject's aesthetic appearance of the lower face, i.e. the treated area, compared to the photographs taken before treatment?" The shall rate according to the left column in Table 3 and the Investigator shall rate according to the right column in Table 3, the scores for and Investigator rating are comparable.

A clinically significant improvement is defined as a score of improved; much improved; or very much improved. The GAIS assessments shall as far as possible be performed by the same Investigator throughout the study.

Naturalness,

[figure not shown]
will answer the questions regarding naturalness, Both the Investigator and according to Appendix 5 (Investigator's questionnaire) and Appendix 6 respectively.

Doc id 05DF1910 Clinical Study Protocol 🚣 GALDERMA MA-42248

Subject Satisfaction Questionnaire

The subjects will assess subject satisfaction, result at visit 2 – 5 (baseline, week 3, 6 and 9), before treatment with study product, when applicable (Appendix 9). Question 1, 2, 3 and 6 will be removed from the baseline questionnaire and question 2 from week 3.

Safety Assessments

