10.1 Analysis populations

The following populations will be defined:

Includes all subjects who were injected with study Safety

product.

Includes all treatment compliant subjects, i.e. subjects Modified Intention-totreated at both baseline and 3 weeks. treat (MITT)

All efficacy analyses will be based on the MITT population. Safety analysis is performed based on the safety population set.

The disposition of subjects will be presented in tables and/or figures as appropriate. The number of screened, treated, completed, and withdrawn subjects will be presented, as well as number of subjects in each analysis population set.

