Appendix 9 Subject satisfaction questionnaire

- 1 My first treatment improved my appearance
- 2 Compared to my first treatment, treating both areas in combination improved my appearance
- 3 I am satisfied with the contour of my lower face after treatment
- 4 I am satisfied with the shape of my chin
- 5 I am satisfied with how well defined my chin looks
- 6 I feel more attractive after treatment
- 7 I feel comfortable being photographed

Title 05DF1910 Clinical Study Protocol Doc id 👶 GALDERMA MA-42248

Title 05DF1910 Clinical Study Protocol

Doc id

Print date:

MA-42248

2022-10-28 09:19

SIGNATURES PAGE

Date	Signed by			
2020-09-24 06:18	PPD			
Justification	Approved by Technical Expert			
2020-09-24 06:38	PPD			
Justification	Approved by Technical Expert			
2020-09-24 06:52	PPD			
Justification	Approved by Project Manager			
2020-09-24 09:16	PPD			
Justification	Approved by Technical Expert			
2020-10-02 11:10	PPD			
Justification	Approved by PPD			

Effective date: 2020-10-02 11:10

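### Does the GAIS analysis in section 10.3 need a paired week-3 to week-6 summary to describe the stepwise treatment?

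*Combined protocol and SAP*

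**What the plan says.** Section 10.3 has all analyses done by treatment group and in total. For GAIS it states: "The GAIS assessment will be presented in frequency tables at each follow-up visit and for each evaluator separately". It adds the proportion of subjects at improved or better. That cut is not arbitrary, because section 7.3 says: "A clinically significant improvement is defined as a score of improved; much improved; or very much improved". The 10.3 sentence introducing this proportion then stops mid-clause, and the Statistical Method row of the synopsis is redacted.

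Three other provisions matter:

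- **Timing of the ratings.** Section 7.1 says: "At treatment visits, all assessments must be performed before study treatment is administered". Appendix 4 takes the pre-treatment baseline photograph as the reference.
- **Population.** Section 10.1 says: "All efficacy analyses will be based on the MITT population". That population is the subjects treated at both baseline and week 3.
- **The subject's own view of the step.** Appendix 9 item 2 reads: "Compared to my first treatment, treating both areas in combination improved my appearance". Section 7.6 fixes when it is asked: "Question 1, 2, 3 and 6 will be removed from the baseline questionnaire and question 2 from week 3". Item 2 is therefore answered at weeks 6 and 9.

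**The concern.** Each subject is rated at week 3 with one area treated and at week 6 with both treated and no touch-up yet given, against the same baseline photograph. The design creates a within-subject pair, and the readable analysis tabulates the two halves separately. Separate tables fix the net movement between grades but not who moved. The improved-or-better proportion cannot register movement among the top three grades. For a study that sets out to document a stepwise course and to inform treatment guidelines (section 2.3), a reader may want to know how many subjects the evaluator rated better, the same or worse after the second step. If that number were needed for a stated aim, the plan would fall short of it.

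**Working it through.** The plan has no figure to reproduce here: section 10.8 says the sample size rests on no calculation. The check has two parts.

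**1. What the separate tables leave open.** The inputs are assumed grade counts for one group of 30 (the planned group size in 10.8), in the order very much improved / much improved / improved / no change / worse. Take week 3 as 3/10/14/3/0 and week 6 as 8/12/7/3/0. Improved or better is 27/30 (90%) at both visits.

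Subjects at or above each grade, week 6 minus week 3:

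- very much improved: 8 − 3 = 5
- much improved or better: 20 − 13 = 7
- improved or better: 27 − 27 = 0

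From these:

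- Net grade steps gained = 5 + 7 + 0 = 12. The tables fix this.
- Fewest gainers = largest single difference = 7 (5 move two grades, 2 move one: 5×2 + 2 = 12).
- Most gainers if nobody worsens = 12, one step each.
- Most gainers with no limit = 8 + 12 + 3 = 23. Gainers can fill every week-6 place in the top two grades, but only the 3 subjects at no change in week 3 can rise into improved. Reaching 23 requires at least 5 of 30 to worsen.

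The width depends on the assumed counts:

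| Week 3 → week 6 | Gainers, none worsening | Gainers, no limit |
|---|---|---|
| 3/10/14/3/0 → 8/12/7/3/0 | 7–12 | 7–23 |
| 3/10/14/3/0 → 6/11/10/3/0 | 4–7 | 4–20 |
| 0/3/24/3/0 → 0/10/17/3/0 | 7 | 7–13 |
| 20/8/2/0/0 → 26/4/0/0/0 | 6–8 | 6–10 |

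The ambiguity is real but varies. It is small when ratings cluster and few subjects worsen. In the first example the planned five-grade tables still show the improvement: much improved or better rises from 13/30 to 20/30.

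**2. Whether any stated aim needs the missing count.** Set the aims beside the tables.

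- The synopsis objective is improvement from the chin, from the nasolabial folds and marionette lines, and from both. The down-up table at week 3 gives chin only, the top-down table at week 3 gives folds and lines only, and both groups' week-6 tables give the combination.
- The GAIS endpoint (synopsis and 3.1.1) is the rating at weeks 3, 6 and 9. It is not a change between visits.
- Section 2.3 goes beyond documenting the stepwise course: it asks whether the down-up or top-down order affects the endpoints. That comparison is between groups at a given visit, and the tables by group supply it. A shift table within each group does not.
- Item 2 of the questionnaire already asks each subject about the step, and 10.3 reports agreement with the agreement-scale items.

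**What the extra count would be worth.** With 95% Wilson intervals, 7/30 gaining is 23% (12–41%) and 12/30 is 40% (25–58%). The widths are 0.409 − 0.118 = 0.291 and 0.577 − 0.246 = 0.331. On Table 1's schedule the change also includes three more weeks since the first injection. Section 4.1 places visit 4 six weeks after the second treatment, which does not match Table 1. The two need reconciling, but on either reading week 6 follows both treatments.

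**The case for a change.** The best argument for adding the table is that it costs almost nothing. The scores are collected, the population is restricted to subjects who had both treatments, and one sentence with one small table per group and evaluator would replace a range by a count. Item 2 is the subject's retrospective opinion and not an evaluator's grade. Observed-case reporting (10.5) lets the two visits cover slightly different subjects, which would loosen the bounds further. Section 10.6 allows data to be analysed before completion, so specifying a paired table now would keep it from being a later choice.

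All of that stands as a case for an optional table. None of it shows that a planned result would be wrong or a stated question left unanswered. The count would also be hard to interpret. The treating Investigator knows the treatment (4.4.3). Section 7.3 introduces the scale with the words "While GAIS is neither an objective measurement tool nor a validated tool". The protocol gives no meaning to a one-grade change; its only threshold is improved or better, which is already reported. Finally, the text is missing immediately after the planned GAIS summaries, where a further one could sit, and redacted text cannot be counted as an omission.

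**Conclusion.** The concern does not hold. Followed as written, the plan gives each group's full grade distribution with one area treated and with both, which is what the stated objective asks for, and it supports the down-up versus top-down comparison. What the readable text leaves out is a descriptive count: in the assumed example, 7 to 12 gainers of 30 if nobody worsens and 7 to 23 at the extreme, with narrower ranges for clustered ratings. No planned estimate or conclusion depends on that count. The bounds rest on assumed grade counts and on the same 30 subjects being scored at both visits. The judgement that nothing is missing covers the readable objectives, endpoints and analyses only. A shift table could be added as a matter of preference, but the plan does not need it.

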	Approximately 60 subjects (of which at least 20 males) will be enrolled and randomized into two groups. Stratification for site and gender will be performed. Both groups will be stepwise treated in the chin and nasolabial folds (NLF)/marionette lines (ML). One group will start treatment in chin (at baseline), followed by treatment in NLFs and MLs at week 3. The other group will start treatment in NLFs and MLs at baseline, followed by treatment in chin at week 3. The two groups are referred to as down-up and top-down, respectively.	
	An optional touch-up will be provided at week 6 for all subjects and treatment areas that have not obtained optimal aesthetic improvement as agreed between subject and Investigator. Subjects will be followed until week 9.	
	Study assessments, such as questionnaires, must be completed before treatment if injection is planned at the visit (applicable for baseline, week 3 and week 6 [if touch-up will be performed]).	
Clinical Study Duration:	First subject first visit to last subject last visit will be approximately 24 weeks: 12 weeks enrolment 3 weeks screening 9 week follow up	
Effectiveness Objectives and Endpoints:	Objective To evaluate aesthetic improvement after treatment in chin and NLFs/MLs, respectively, and in combination. Endpoint and Treating Investigator assessment using the Global Aesthetic Improvement Scale (GAIS) at week 3, 6 and 9.	

Doc id 05DF1910 Clinical Study Protocol GALDERMA MA-42248

Title 05DF1910 Clinical Study Protocol Doc id 👶 GALDERMA MA-42248

	CCI
Safety Objectives and Endpoints:	To evaluate Adverse Events (AEs) collected throughout the study. Device deficiencies will be assessed at treatment visits.
Inclusion Criteria:	Subjects willing to comply with the requirements of the study and providing a signed written informed consent.
	Subjects willing to undergo augmentation and correction therapy in the studied indications
	 Subjects willing to abstain from any other facial plastic surgical or cosmetic procedures for the duration of the study (e.g., laser or chemical resurfacing, facelift, etc.).
	 Adult males or non-pregnant, non-breastfeeding females and women of non-child bearing potential over the age of 21.
	 Urinary pregnancy test must be negative for females of childbearing potential at screening and all injection visits.
	Definition of non-child bearing potential:

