2.2.1.2 Clinical documentation

The first injectable OBT gel product was CE-marked in Europe in 2009. Several studies have been conducted to assess the safety and efficacy of OBT products in the treatment of e.g. cheeks, NLFs, and lips 6-10.

Study rationale and justification for design 2.3

This study aims to document the results of a stepwise treatment and determine if any of the two approaches to be used in this study, down-up and top-down, affects the studied endpoints. Results from the study will be the basis for future treatment guidelines used by aesthetic health care practitioners when injecting Restylane Defyne in the chin, NLF and ML.

Approximately 60 subjects (of which at least 20 males) will be enrolled and randomized into two groups with different treatment schedules. Comparison between the two groups will help to determine if the different treatment approaches affects the outcome, such as subject satisfaction.

Risks and benefits

After the injection of the study products, some common injection-related reactions might occur. These reactions include erythema, swelling, pain, itching, bruising or tenderness at the implant site. Typically, resolution is spontaneous within a few days after injection.

There is a risk that the subject will not gain the full aesthetic correction of the treated areas. There is also a risk for development of palpable HA lumps or displacement of the injected HA. Inflammation or infection has been reported in a few cases after treatment. There may be risk of bruising and/or damaging body structures such as nerves or blood vessels connected to the injection site, however these risks are minor.

Following facial aesthetic treatments isolated rare cases have been reported regarding ischemic events affecting the eye leading to visual loss, and the brain resulting in cerebral infarction. Detailed information on reported adverse events (AE) relevant for the study product is provided in the instructions for use (IFU).

Lidocaine can in rare cases give allergic reactions, and therefore subjects with known allergy or hypersensitivity to local anaesthetics should not be included in the study.

Given the anticipated low level of transient and acceptable AEs in connection with the injection, the risk-benefit assessment of the use of the study products for lower face augmentation offers a potential clinical benefit, such as subject rated improvement of attractiveness and satisfaction, at reasonable risk.

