3.1 Objectives and endpoints

3.1.1 Effectiveness objectives and endpoints

Objective

Endpoint

and Treating Investigator assessment using the Global Aesthetic Improvement Scale at week 3, 6 and 9.

Objective

To evaluate naturalness of the treatment result

Endpoint

Assessed by and Treating Investigator using directed questions at week 3, 6 and 9.

Objective

To evaluate subject satisfaction treating chin versus treating NLF/ML, respectively, and in combination.

Endpoint

MA-42248.doc

Doc id 05DF1910 Clinical Study Protocol 🚣 GALDERMA MA-42248

Subject assessment using subject satisfaction questionnaire and at baseline, week 3, 6 and 9.

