3.1.2 Safety objective and endpoints

Objective:

To evaluate AEs collected throughout the study

Endpoint

Incidence, intensity, duration and onset of AEs collected from injection of study product to patient withdrawal or end of study (visit 5).

Design of the Study

General outline

This is a 12-week, randomized, male-female and site stratified, evaluator-blinded, multicentre study to evaluate the effectiveness and safety of Restylane Defyne when using two different injection approaches, stepwise down-up vs. top-down, when treating the lower face.

Approximately 60 subjects requiring augmentation and correction therapy in the chin, NLFs and MLs fulfilling all eligibility criteria will be enrolled in the study. The subjects will be randomized to one of two treatment groups, the first treatment group will receive injections in the chin area at baseline and in the NLFs and MLs at the visit 3 (week 3), the second group will undergo the same treatment but in reverse order. The two groups are referred to as downup and top-down. Male-female stratification will be applied in the randomization and the aim is to randomize 10 male subjects to each group.

[figure not shown]
Doe id 05DF1910 Clinical Study Protocol 🚣 GALDERMA MA-42248

Six weeks after the second treatment, at visit 4, an optional touch-up will be administered to subjects that have not obtained optimal aesthetic improvement as agreed between subject and Investigator.

The subject will return to the clinic for a final follow-up visit (visit 5) 9 weeks after the first treatment.

All efficacy study assessments will be performed before treatment and safety will be followed by AE and device deficiency reporting throughout the study.

The Investigator will assess, Global Aesthetic Improvement Scale (GAIS), naturalness/ and safety. The subject assessments include, subject satisfaction questionnaire.

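### Section 2.3 looks to a comparison of down-up with top-down on satisfaction, but the visible satisfaction text of 10.3 gives no between-group difference or interval and names no item or visit for it

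*Combined protocol and SAP*

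**What the plan says.** Section 2.3 (Study rationale and justification for design) sets an aim about treatment order: "Comparison between the two groups will help to determine if the different treatment approaches affects the outcome, such as subject satisfaction". It also says what the answer is for: "Results from the study will be the basis for future treatment guidelines used by aesthetic health care practitioners". The General outline in section 4 describes the evaluation in the same terms: "when using two different injection approaches, stepwise down-up vs. top-down, when treating the lower face". Section 4.4.1 randomises subjects to the two approaches, stratified by site and gender.

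The formal satisfaction objective in 3.1.1 is a different question, about area and combination: "To evaluate subject satisfaction treating chin versus treating NLF/ML, respectively, and in combination".

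For analysis, 10.3 opens with "All analyses will be performed by treatment group and in total". Its satisfaction text is two sentences: "The subject satisfaction questionnaire assessments will be presented in frequency tables at each applicable visit", and, for questions answered on an agreement scale, "the number and percentage of subjects agreeing (Definitely agree/Somewhat agree) to the assessment will also be presented". Section 10.8 says that the sample size of about 60 (30 per group) does not come from a calculation. Efficacy uses the MITT population, meaning subjects treated at both baseline and week 3 (10.1), on observed cases without imputation (10.5).

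**The concern.** The area and combination objective in 3.1.1 is served descriptively by the planned tables. The order aim in 2.3 is not served in the same way. It asks whether one randomised group differs from the other, and the quantity that answers it is a between-group difference with a statement of its precision. The visible satisfaction text gives two percentages and leaves the reader to compare them by eye.

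Two errors then become easy. Similar percentages may be read as showing that order makes no difference, when the data still allow a sizeable one. Or a chance gap on one of several items and visits may be singled out after the results are known. Either matters more because the results are meant to inform treatment guidelines.

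**Working it through.** **Which results can speak to order.** Appendix 9 has seven questions. Section 7.6 drops questions 1, 2, 3 and 6 at baseline and question 2 at week 3. The synopsis says "Study assessments, such as questionnaires, must be completed before treatment if injection is planned at the visit", so at week 3 each group has had only one area treated.

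- Week 3: 7 - 1 = 6 item results, all contrasting chin with NLF/ML. These belong to the 3.1.1 objective.
- Questions 1 and 2 at weeks 6 and 9: 2 x 2 = 4 results. Both refer to the first treatment, which differs between groups, so they also concern area or combination.
- Questions 3 to 7 at weeks 6 and 9: 5 x 2 = 10 results. They read the same in both groups after both areas have been treated. These ten can carry the order question, and 10.3 singles out none of them.

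**Inputs for precision.** The plan has no figure to reproduce. The 30 per group is from 10.8. The agreement levels of 50%, 80% and 90% are assumptions, since the documents give none. So is a 10% loss from the analysis set, giving 30 x 0.9 = 27 per group.

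**Wald half-width of a 95% interval for the difference**, 1.96 x sqrt(2p(1-p)/n):

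| Agreement p | n = 30 | n = 27 |
|---|---|---|
| 50% | 1.96 x sqrt(0.50/30) = 25.3 points | 26.7 points |
| 80% | 1.96 x sqrt(0.32/30) = 20.2 points | 21.3 points |
| 90% | 1.96 x sqrt(0.18/30) = 15.2 points | 16.0 points |

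**Newcombe check**, better suited to high percentages. With Wilson limits (l, u) for each group and d = p1 - p2:

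lower = d - sqrt((p1 - l1)^2 + (u2 - p2)^2); upper = d + sqrt((u1 - p1)^2 + (p2 - l2)^2)

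For 27/30 the Wilson limits are 0.744 and 0.965. With 27/30 in both groups, d = 0 and the half-width is sqrt(0.156^2 + 0.065^2) = 0.169. For 24/30 the limits are 0.627 and 0.905, and with 24/30 in both groups the half-width is sqrt(0.173^2 + 0.105^2) = 0.202.

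| Agreeing, group 1 v group 2 | Difference | Newcombe 95% interval |
|---|---|---|
| 27/30 v 27/30 | 0 | -17 to +17 points |
| 24/30 v 24/30 | 0 | -20 to +20 points |
| 27/30 v 24/30 | 10 points | -9 to +29 points |
| 27/30 v 21/30 | 20 points | -0.5 to +39 points |
| 27/30 v 20/30 | 23 points | +2 to +42 points |

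Against 27/30, zero is first excluded at 20/30.

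**How often a real gap would look small.** If true agreement were 90% and 75% (assumed), the exact binomial probability that the observed percentages lie within 3/30, or 10 points, of each other is 0.363. About 36% of such trials would show groups that look similar.

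**The case against.** The strongest objection is that the absence cannot be established. The synopsis Statistical Method entry is blacked out, the GAIS sentence in 10.3 breaks off before naming what accompanies the proportion improved, and the satisfaction endpoint in 3.1.1 has a gap. A general sentence on group differences could sit in any of these. This stands as a limit. A reader might infer that the plan contains no between-group comparison at all, and the documents do not support that. What can be said is that the two satisfaction sentences read as complete and contain none.

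Second, this is a descriptive post-market study. Its formal satisfaction objective is met, 10.8 makes no claim to power, and section 2.3 says only that the comparison will help. This stands against asking for a hypothesis test or a larger sample. It does not remove the gap, because a difference with an interval is itself descriptive estimation.

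Third, by-group counts are planned for agreement-scale questions, so any reader could compute the interval. That is true, but the item and visit would then be chosen with the results in view.

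A reader might also infer that the study cannot show whether order matters. That goes too far: 27/30 against 20/30 would exclude zero.

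**Conclusion.** The concern holds for the visible satisfaction text. Section 2.3 gives the group comparison a purpose, and 10.3 supplies neither the estimate nor its precision for satisfaction, and fixes no item or visit for it. At 30 per group the unstated uncertainty is roughly 15 to 25 points either way, and identical results at 27/30 leave -17 to +17 points open. These sizes rest on the assumed agreement levels. The finding also depends on there being no general comparison in the redacted text, so confidence is medium. It calls for an inexpensive improvement to the analysis and does not invalidate the design.

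It would also be wrong to treat the added comparison as protected by randomisation alone. The MITT condition (treated at both visits) and the observed-case rule both act after randomisation.

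**What to change.** First, the sponsor should confirm whether the redacted Statistical Method entry or the redacted parts of 10.3 already give a between-group comparison for satisfaction. If not, add to 10.3:

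- An exploratory down-up minus top-down difference in percentage agreeing, with a 95% confidence interval (for example Newcombe), for one item and visit fixed before the data are analysed. Question 3 (lower-face contour) at week 6 before touch-up is a suitable example, provided it uses the agreement scale; Appendix 9 shows no response options.
- The same estimate for questions 4 to 7 and for week 9, which includes any touch-up, labelled supportive.
- A statement that an interval including zero is not evidence that the two orders give equal results. No equivalence margin is suggested, because the documents provide no basis for one.
- The number randomised and the number analysed per group, shown beside the estimate.
- A label on the week 3 contrasts and on questions 1 and 2, saying that they serve the 3.1.1 objective.

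The cost is analysis wording and a few tables, with no new subjects or data. There are downsides to state openly. The interval will be wide. Question 3 is not asked at baseline, so there is no baseline value to adjust for. Order is tied to time since each area's injection: on the timing in Table 1, one area is at six weeks and the other at three, reversed between groups. The General outline instead places visit 4 six weeks after the second treatment, and the two passages must be reconciled so that the week 6 comparison has one meaning.
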